6.3.1. Stratification

If participants are eligible for more than one ISA, they will be randomly assigned to an ISA using the IWRS. Participation in an ISA is not decided by the site, participant, or physician.

CCI [REDACTED]

Each ISA will include a stratification factor based on the average baseline pain severity score as measured by the NRS.

The definition of the stratification factor is provided as:

- severe pain: ≥ 7 on the baseline NRS average pain score, or
- moderate pain: < 7 on the baseline NRS average pain score.

Additional stratification factors may be defined in the ISA or DSA.

6.4. Study Intervention Compliance

When required, study intervention will be administered under medical supervision by the investigator or designee. The date and time of each dose administered will be recorded in the source documents and recorded in the case report form (CRF). The dose of study intervention and study participant identification will be confirmed prior to the time of dosing.

When participants self-administer study intervention(s) at home, compliance with study intervention will be assessed at each visit. Compliance will be assessed by direct questioning and counting returned study intervention per each ISA and documented in the source documents and CRF.

Additional information on intervention compliance will be in the ISA.

6.5. Concomitant Therapy

Any medication or vaccine, including over-the-counter or prescription medicines, vitamins, and/or herbal supplements, that the participant is receiving at the time of enrollment or receives during the study must be recorded along with the

- reason for use
- dates of administration including start and end dates, and
- dose and frequency.

Permitted Medication

Permitted concomitant therapy should remain stable for dosing and frequency of use throughout the treatment period. The Medical Monitor should be contacted if there are any questions regarding concomitant therapy.

Medically required changes to concomitant medication not taken for pain may be considered on a case-by-case basis with the documented approval of the Medical Monitor.

Short-term use of medications such as analgesics or corticosteroids is permitted to treat medical conditions other than chronic pain for no more than a total of 7 days during the treatment phase. For these situations contact the Medical Monitor.

Rescue Medication

Permitted Rescue Medication

Acetaminophen is the **ONLY** allowed rescue medication.

Maximum Daily Acetaminophen Dose

The maximum daily dose is 3000 mg per day.

This maximum amount is inclusive of combination products in which acetaminophen is contained.

General guidelines for acetaminophen use and recording the dose

Beginning at Visit 2, participants will record their use and maximum total dose of acetaminophen daily using a take-home device.

Rescue medication should be used at the lowest effective dose for the shortest duration possible throughout study participation.

During the minimum required 7 days of the PDEP, limit use to no more than 4 days.

This table describes acetaminophen use guidance during the double-blind treatment period.

Acetaminophen Use Guidance during Visit 3 through Visit 7	
Maximum dose per day	3000 mg
Maximum consecutive days	3 days
Maximum total days	14 days

The investigative site should evaluate appropriateness of rescue medication use at each visit. Continued education should be provided as necessary.

Prohibited Medication

Medications for pain other than protocol permitted rescue medication are prohibited after Visit 2.

Any investigational intervention judged to be scientifically or medically incompatible with this study is prohibited.

These restrictions may not apply during follow-up periods in which investigational interventions are not taken. Any modifications to restrictions will be specified in the ISA.

Additional information about concomitant medication use is provided in the respective ISA.

6.6. Dose Modification

This section is not applicable for the master protocol.

6.7. Intervention after the End of the Study

No continued access is planned after completion of each proof-of-concept master protocol ISA, as additional efficacy would be needed to demonstrate continued access criteria.

7. Discontinuation of Study Intervention and Participant Discontinuation/Withdrawal

7.1. Discontinuation of Study Intervention

In rare instances, it may be necessary for a participant to permanently discontinue (definitive discontinuation) study intervention.

If study intervention is definitively discontinued, the study participant will not remain in the master protocol or ISA. See the master protocol and ISA SoA for data to be collected at the time of discontinuation of study intervention and follow-up and for any further evaluations that need to be completed.

Additional criteria for discontinuation may be included in each ISA. If an ISA criterion is more restrictive, it should be applied for those participants in the respective ISA.

Participants **may** be discontinued from study intervention if these situations occur:

- based on a specific AE profile, as recommended by the Assessment Committee (AC), the Medical Monitor, or the study sponsor physician/scientist, in discussions with the Principal Investigator
- incorrect enrollment
- severe noncompliance to the study protocol in the judgment of the investigator
- participants answered 'yes' to Question 4 or 5 on the 'Suicidal Ideation' portion of the C-SSRS, or
- participants answered 'yes' to any of the suicide-related behaviors on the Suicidal Behavior portion of the C-SSRS.
 - a psychiatrist or appropriately trained professional may assist in the decision to discontinue the participant for C-SSRS responses.

Liver Safety

Discontinuation of the intervention should be considered when a participant meets one of the following conditions after consultation with the sponsor-designated Medical Monitor.

- ALT or AST $>8 \times$ ULN
- ALT or AST $>5 \times$ ULN for more than 2 weeks
- ALT or AST $>3 \times$ ULN and either TBL $>2 \times$ ULN or international normalized ratio (INR) >1.5 , or
- ALT or AST $>3 \times$ ULN with the appearance of fatigue, nausea, vomiting, right upper quadrant pain or tenderness, fever, rash, and/or eosinophilia ($>5\%$).

The discontinuation criteria are applicable for participants with no known liver disease and normal or near normal baseline liver tests of

- $ALT < 2 \times ULN$
- $TBL < 1.5 \times ULN$, and
- $ALP < 1.5 \times ULN$.

Cardiovascular Safety

If a clinically significant finding is identified including, but not limited to, changes from baseline in QTcF after enrollment, the investigator or qualified designee will determine if the study participant can continue in the master protocol or ISA, and if any change in study participant management is needed.

This review of the ECG printed at the time of collection must be documented. Any new clinically relevant finding should be reported as an AE.

7.2. Participant Discontinuation/Withdrawal from the Study

A participant may withdraw from the master protocol or ISA:

- at any time at his/her own request
- at the request of his/her designee (for example, parents or legal guardian)
- at the discretion of the investigator for safety, behavioral, compliance, or administrative reasons
- if the participant becomes pregnant
- if enrollment in any other clinical study involving an investigational intervention or enrollment in any other type of medical research judged not to be scientifically or medically compatible with the master protocol or ISA, or
- if the participant, for any reason, requires treatment with another therapeutic agent that has been demonstrated to be effective for treatment of the study indication, discontinuation should occur prior to introduction of the new agent.

Discontinuation is expected to be uncommon.

If possible, an early discontinuation visit should be conducted at the time of discontinuing from the master protocol/DSA or an ISA. Data to be collected at the time of study discontinuation and follow-up and for any further evaluations that need to be completed will be included in the master protocol/DSA and ISA. The participant will be permanently discontinued both from the study intervention and from the master protocol/DSA or ISA at that time.

If the participant withdraws consent for disclosure of future information, the sponsor may retain and continue to use any data collected before such a withdrawal of consent. If a participant withdraws from the study, he/she may request destruction of any samples taken and not tested, and the investigator must document this in the site study records.

7.2.1. Discontinuation of Inadvertently Enrolled Participants

If the sponsor or investigator identifies a participant who did not meet enrollment criteria and was inadvertently enrolled in the master protocol/DSA or ISA, then the participant should be

discontinued from study treatment unless there are extenuating circumstances that make it medically necessary for the participant to continue on study treatment.

If the investigator and the sponsor clinical research physician agree that it is medically appropriate to continue, the investigator must obtain documented approval from the sponsor to allow the inadvertently enrolled participant to continue in the master protocol or ISA with or without treatment with investigational intervention.

Safety follow-up is outlined in

Section 1.3 (Schedule of Activities [SoA])

Section 8.2 (Safety Assessments), and

Section 8.3 (Adverse Events and Serious Adverse Events).

7.3. Lost to Follow-Up

A participant will be considered lost to follow-up if he or she repeatedly fails to return for scheduled visits and is unable to be contacted by the study site. Study personnel or designee are expected to make diligent attempts to contact participants who fail to return for a scheduled visit or were otherwise unable to be followed up by the site.

Information about the discontinuation of specific sites or of the study are handled as part of the regulatory, ethical, and trial oversight considerations in Appendix 1.

8. Study Assessments and Procedures

Master protocol procedures and their timing are summarized in the SoA (Section 1.3). Additional SoAs are included in the DSA and may also be included in each ISA.

Protocol waivers or exemptions are not allowed.

Immediate safety concerns should be discussed with the sponsor immediately upon occurrence or awareness to determine if the participant should continue or discontinue study intervention.

Adherence to the study design requirements, including those specified in the SoA, is essential and required for study conduct.

All screening evaluations must be completed and reviewed to confirm that potential participants meet all eligibility criteria for the master protocol, DSA, and each active ISA. The investigator will maintain a screening log to record details of all participants screened and to confirm eligibility or record reasons for screening failure, as applicable.

Self-reported questionnaires will be administered by either an electronic device or on paper. Participants' self-assessments should be completed before any clinical examinations are performed.

8.1. Efficacy Assessments

The master protocol contains a core set of assessments based on the IMMPACT guidelines (Dworkin et. al. 2005). This table describes the assessments and corresponding measures.

Core Assessment	Measure
Pain intensity	Visual Analog Scale (VAS)* for pain
Pain intensity	Numeric Rating Scale (NRS)* for pain
Participant ratings of overall improvement	Patient Global Impression of Change (PGI)*
Emotional functioning	EuroQol-5D 5 level questionnaire (EQ-5D-5L)*
Quality of sleep	Medical Outcomes Study (MOS) Sleep Scale*
Physical functioning	Described in each disease-state addendum

* = common endpoint measure across all pain types.

8.1.1. Screening and Preliminary Data Entry Period

Visual Analog Scale

The VAS for pain will be used at screening and at each clinic visit. This is a graphic, single-item scale where participants are asked to describe their pain intensity over the past week, in the area under study, on a scale of 0 to 100:

0 = no pain, and

100 = worst imaginable pain.

Participants complete the VAS by placing a line perpendicular to the VAS line at a point that describes their pain intensity. Inclusion criteria are described in Section 5.1.

Numeric Rating Scale

The NRS will be used during the PDEP and daily throughout the study to describe pain severity. This is a numeric, single-item scale where participants are asked to describe their average and worst pain over the past 24 hours, on a scale of 0 to 10:

0 = no pain, and

10 = pain as bad as you can imagine.

Participants complete the NRS daily using a take-home device. Inclusion criteria for the PDEP are described in Section 5.1. Participant compliance is reviewed at each clinic visit.

8.1.2. Primary Efficacy Outcome Measure–Pain Intensity using Numeric Rating Scale

The NRS is used across all disease states to assess pain intensity.

The primary outcome measure is the mean change from baseline to endpoint for average pain intensity as assessed by the NRS item

‘Please rate your pain by selecting the one number [0-10] that describes your AVERAGE level of [area under study] pain during the past 24 hours.’

This measure was selected based on its demonstrated ability to detect changes in pain and its common use across the disease states under study.

Participants complete the NRS daily using a take-home device. Compliance is reviewed at each clinic visit.

8.1.3. Secondary Efficacy Outcome Measures

8.1.3.1. Numeric Rating Scale

A secondary measure is the mean change from baseline to endpoint for worst pain intensity as measured by the NRS item

‘Please rate your pain by selecting the one number [0-10] that describes your WORST level of [area under study] pain during the past 24 hours.’

8.1.3.2. Participant Ratings on Overall Improvement

The Patient Global Impression of Change (PGI) is used across all disease states. It captures the participant’s perspective of treatment apart from sub-aspects of the general improvement.

This is a numeric scale from 1 to 7:

1 = very much better, and

7 = very much worse.

The participant is asked to

‘Mark the box that best describes how your pain symptoms are now, compared to how they were before you started taking this medicine.’

8.1.3.3. Emotional Functioning Assessments

The EQ-5D-5L health status questionnaire is used across all disease states.

The EQ-5D-5L is one of the most popular patient-completed instruments to address quality of life (Buchholz et. al. 2018). It is a descriptive system that includes 5 dimensions:

- mobility
- self-care
- usual activities
- pain/discomfort, and
- anxiety/depression.

The participant is asked to ‘check the ONE box that best describes your health TODAY,’ choosing from 5 options provided under each dimension. The scores on the 5 dimensions can be presented as a health profile or converted to a single summary index number.

The EQ-5D-5L also includes the EQ VAS, which records the participant’s self-rated health on a vertical VAS of 0 to 100:

0 = the worst health you can imagine, and

100 = the best health you can imagine.

The instrument used in its EQ-5D-5L version is a short, reliable, validated, easy-to-complete scale with excellent test-retest reliability to address quality of life in relation to pain due to several diseases.

8.1.3.4. Sleep Quality

Sleep disturbance is an important issue in pain research. Among various available instruments, the Medical Outcome Study (MOS) Sleep Scale provides a unique, psychometrically validated score for sleep disturbance.

This scale consists of 12 questions addressing the past week. Participants report how often each sleep symptom or problem is present on a 5-point categorical scale ranging from ‘all of the time’ to ‘none of the time.’ The question about time to fall asleep is reported by a 5-point categorical scale and the quantity of sleep is reported as the average number of hours slept each night.

This scale has low administration burden, has been used in different pain studies, and has been validated in patients with neuropathic pain.

8.2. Safety Assessments

Planned time points for safety assessments are provided in the SoA (Section 1.3).

Standard safety assessments include

- physical examination
- vital sign and body weight measurements
- 12-lead ECGs
- clinical laboratory tests
- hepatic safety monitoring (Appendix 6, Section 10.6)
- C-SSRS, and

- spontaneously reported AEs.

8.2.1. Physical Examinations

A complete physical examination will be conducted at Visit 1, as specified in the SoA. Symptom-directed physical examinations may also be conducted at other visits, as determined by the investigator, if a participant presents with complaints.

8.2.2. Vital Signs

Vital signs (blood pressure, pulse rate, body temperature) will be measured with the participant in a sitting position, as specified in the SoA and as clinically indicated. Additional vital signs may be measured during the study visits if warranted, as determined by the investigator, or as detailed in the respective ISAs.

8.2.3. Electrocardiograms

Evaluating ECGs

Triplicate 12-lead ECGs will be collected as specified in the SoA and as clinically indicated using an ECG machine that automatically calculates the heart rate and measures pulse rate, RR, QRS, QT, and QTcF intervals. Post randomization ECGs will be included in the ISA.

The ECGs should be collected

- before any blood draws, procedures, or meals
- after the participant is supine for at least 5 minutes
- while the participant is supine, and
- as closely as possible in succession, approximately 1 minute apart.

Electrocardiograms may be obtained at additional times, when deemed clinically necessary. Collection of more replicates than expected at a particular time point is allowed to ensure high quality records.

A qualified physician (the investigator or qualified designee) at the site will interpret the ECGs as soon after the time of ECG collection as possible and ideally while the participant is still present.

If a clinically significant quantitative or qualitative change from baseline is identified after enrollment, the investigator or qualified designee will

1. assess the participant for symptoms (for example, palpitations, near syncope, syncope)
2. determine if any change in participant management is needed
3. determine if the participant can continue the study, and
4. document the review of the ECG printed at the time of evaluation from at least 1 of the replicate ECGs from each time point.

Transmitting and Overreading Electrocardiogram Data

Digital ECGs will be transmitted electronically to a central ECG laboratory designated by Lilly. A cardiologist at the central ECG laboratory will then conduct a full overread of the replicate ECGs (including all intervals). A report based on data from this overread will be issued

to the investigative site. All data from the overreads will be placed in the Lilly database for analytical and study report purposes.

If there are differences in ECG interpretation between the investigator or qualified designee and the cardiologist at the central ECG laboratory, the interpretation by the investigator or qualified designee will be used for study entry and immediate participant management. Interpretations from the cardiologist at the central ECG laboratory will be used for data analysis and report writing purposes.

The investigator or qualified designee must document the review of the final overread ECG report issued by the central ECG laboratory and any alert reports.

8.2.4. Clinical Safety Laboratory Assessments

See Appendix 2 for the list of clinical laboratory tests to be performed and the SoA (Section 1.3) for the timing and frequency. All protocol-required laboratory assessments, as defined in Appendix 2, must be conducted in accordance with standard collection requirements, the laboratory manual and the SoA.

The investigator must

- review the laboratory results,
- document this review, and
- report any clinically relevant changes occurring during the study as an AE.

The laboratory results must be retained with the source documents unless a Source Document Agreement or comparable document cites an electronic location that accommodates the expected retention duration. Clinically significant abnormal laboratory findings are those which are not associated with the underlying disease, unless judged by the investigator to be more severe than expected for the participant's condition.

All laboratory tests with values considered clinically significantly abnormal during participation in the master protocol or ISA should be repeated until the values return to normal or baseline, or are no longer considered clinically significant by the investigator or Medical Monitor.

If such values do not return to normal or baseline within a period judged reasonable by the investigator, the etiology should be identified and the sponsor notified.

If laboratory values from nonprotocol-specified laboratory assessments performed at an investigator-designated local laboratory require a change in participant management or are considered clinically significant by the investigator (for example, SAE or AE or dose modification), then report the information as an AE.

8.2.5. Hepatic Safety Monitoring

Additional monitoring may be included in each ISA. If monitoring is more restrictive in the ISA, then it should be applied for those participants in the respective ISA.

Close Hepatic Monitoring

This table describes when close hepatic monitoring should occur.

If a participant with baseline...	has the following elevations...
ALT or AST <1.5 × ULN ALP <1.5 × ULN TBL <1.5 × ULN	ALT or AST ≥3 × ULN ALP ≥2 × ULN TBL ≥2 × ULN, except for those with Gilbert's syndrome
ALT or AST ≥1.5 × ULN ALP ≥1.5 × ULN TBL ≥1.5 × ULN	ALT or AST ≥2 × baseline ALP ≥2 × baseline TBL ≥2 × baseline, except for those with Gilbert's syndrome

Abbreviations: ALP = alkaline phosphatase; ALT = alanine aminotransferase; AST = aspartate aminotransferase; TBL = total bilirubin; ULN = upper limit of normal.

The laboratory tests listed in Appendix 6, including ALT, AST, ALP, TBL, direct bilirubin, gamma-glutamyl transferase, and creatine kinase, should be repeated within 48 to 72 hours to confirm the abnormality and to determine whether it is increasing or decreasing.

If the abnormality persists or worsens, clinical and laboratory monitoring, and evaluation for the possible causes of the abnormal liver tests should be initiated by the investigator in consultation with the sponsor's designated Medical Monitor.

At a minimum, this evaluation should include a physical examination and a thorough medical history, including symptoms, recent illnesses (for example, heart failure, systemic infection, hypotension, seizures) recent travel, history of concomitant medications (including over-the-counter), herbal and dietary supplements, history of alcohol use, and other substance abuse.

Initially, monitoring of symptoms and hepatic biochemical tests should be done at a frequency of 1 to 3 times weekly, based on the participant's clinical condition and hepatic biochemical tests. Subsequently, the frequency of monitoring may be lowered to once every 1 to 2 weeks if the participant's clinical condition and laboratory results stabilize. Monitoring of ALT, AST, ALP, and TBL should continue until levels normalize or return to approximate baseline levels.

Comprehensive Hepatic Evaluation

This table describes when a comprehensive evaluation should occur to search for possible causes of liver injury.

If a participant with baseline...	has the following elevations...
ALT or AST $<1.5 \times$ ULN	ALT or AST $\geq 3 \times$ ULN with hepatic signs/symptoms* OR ALT or AST $\geq 5 \times$ ULN
ALP $<1.5 \times$ ULN	ALP $\geq 3 \times$ ULN
TBL $<1.5 \times$ ULN	TBL $\geq 2 \times$ ULN, except for those with Gilbert's syndrome
ALT or AST $\geq 1.5 \times$ ULN	ALT or AST $\geq 2 \times$ baseline with hepatic signs/symptoms* OR ALT or AST $\geq 3 \times$ baseline
ALP $\geq 1.5 \times$ ULN	ALP $\geq 2 \times$ baseline
TBL $\geq 1.5 \times$ ULN	TBL $\geq 1.5 \times$ baseline, except for those with Gilbert's syndrome

Abbreviations: ALP = alkaline phosphatase; ALT = alanine aminotransferase; AST = aspartate aminotransferase; TBL = total bilirubin; ULN = upper limit of normal.

* Hepatic signs/symptoms are severe fatigue, nausea, vomiting, right upper quadrant abdominal pain, fever, rash, and/or eosinophilia $>5\%$.

At a minimum, this evaluation should include a physical examination and a thorough medical history, as outlined above, as well as tests for prothrombin time (PT-INR); viral hepatitis A, B, C, and E; tests for autoimmune hepatitis; and an abdominal imaging study (for example, ultrasound or computed tomography [CT] scan).

Based on the participant's history and initial results, further testing should be considered in consultation with the sponsor's designated Medical Monitor, including tests for hepatitis D virus, cytomegalovirus, Epstein-Barr virus, acetaminophen levels, acetaminophen protein adducts, urine toxicology screen, Wilson's disease, blood alcohol levels, urinary ethyl glucuronide, and serum phosphatidylethanol.

Based on the circumstances and the investigator's assessment of the participant's clinical condition, the investigator should consider referring the participant for a hepatology/gastroenterology consultation, magnetic resonance cholangiopancreatography (MRCP), endoscopic retrograde cholangiopancreatography (ERCP), cardiac echocardiogram, or liver biopsy.

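### For baseline ALT/AST above 1.5 and below 2 × ULN, Section 8.2.5 starts hepatic monitoring only at 2 × baseline, above the 3 × ULN threshold of Section 7.1

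*Protocol*

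**What the plan says.** Section 7.1 (Liver Safety) lists conditions under which discontinuation should be considered, after consultation with the Medical Monitor. Two of them start at ALT or AST above 3 × ULN. One adds TBL above 2 × ULN "or international normalized ratio (INR) >1.5". The other applies "with the appearance of fatigue, nausea, vomiting, right upper quadrant pain or tenderness, fever, rash, and/or eosinophilia". The criteria cover participants without known liver disease whose baseline ALT is below 2 × ULN, with TBL and ALP below 1.5 × ULN. Section 5.2, criterion 21, excludes ALT or AST of 2 × ULN or more at screening, so a baseline between 1.5 and 2 × ULN is eligible.

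Section 8.2.5 has two tiers, each split by baseline.

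- Baseline below 1.5 × ULN: close monitoring starts at 3 × ULN. The comprehensive evaluation starts at 3 × ULN with symptoms, or at 5 × ULN without.
- Baseline 1.5 × ULN or more: close monitoring starts at "ALT or AST ≥2 × baseline". The comprehensive evaluation starts at twice "baseline with hepatic signs/symptoms", or at three times baseline without symptoms.

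Under close monitoring, and within 48 to 72 hours, "The laboratory tests listed in Appendix 6, including ALT, AST, ALP, TBL, direct bilirubin, gamma-glutamyl transferase, and creatine kinase, should be repeated". The comprehensive tier names a minimum set, "as well as tests for prothrombin time (PT-INR); viral hepatitis A, B, C, and E; tests for autoimmune hepatitis". The section opens by allowing more: "Additional monitoring may be included in each ISA".

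**The concern.** Section 7.1 sets its transaminase threshold in multiples of ULN, whatever the baseline within its range. Section 8.2.5 switches to multiples of baseline at 1.5 × ULN. Above that point twice baseline exceeds 3 × ULN, so the monitoring section can stay silent after the discontinuation section has been reached. With symptoms such as nausea, a Section 7.1 condition is met outright, yet 8.2.5 calls for no 48-to-72-hour repeat, no serial monitoring and no search for a cause. Without symptoms, the INR condition of 7.1 cannot be judged unless someone decides to order an INR, because the Appendix 2 laboratory panel contains no coagulation test. At stake is the consistency of follow-up in a small group with raised baseline enzymes.

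**Working it through.** **Inputs**, in multiples of ULN, with b the baseline of the enzyme concerned:

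- Section 7.1 transaminase threshold: above 3.
- Range of b covered by 7.1 (for ALT) and admitted by criterion 21 (ALT and AST): below 2.
- Section 8.2.5, b ≥ 1.5: close monitoring from 2b; comprehensive tier from 2b with symptoms, from 3b without.

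**Band that triggers neither tier.** A value v passes the 7.1 threshold if v > 3 and triggers neither tier if v < 2b. Symptoms do not change this, because the symptomatic tier also starts at 2b. The band is 3 < v < 2b, with width 2b − 3. It is empty at b = 1.5 and below, and opens as soon as b exceeds 1.5.

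| b | 2b | 3b | Untriggered band | Width 2b − 3 |
|---|---|---|---|---|
| 1.5 | 3.0 | 4.5 | none | 0 |
| 1.6 | 3.2 | 4.8 | >3 to <3.2 | 0.2 |
| 1.75 | 3.5 | 5.25 | >3 to <3.5 | 0.5 |
| 1.9 | 3.8 | 5.7 | >3 to <3.8 | 0.8 |
| 1.99 | 3.98 | 5.97 | >3 to <3.98 | 0.98 |

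**Example.** Take b = 1.9 and ALT 3.5 × ULN with nausea. Since 3.5 > 3, the symptom condition of 7.1 is met. Since 3.5 < 3.8, neither tier of 8.2.5 starts.

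**What closes the band.** With TBL and ALP below 1.5 × ULN at baseline, as 7.1 requires, TBL of 2 × ULN or more triggers both tiers by itself (Gilbert's syndrome excepted), so the bilirubin part of 7.1 is covered. ALP of 2 × ULN or more triggers close monitoring. What remains uncovered is the symptom condition and the INR condition.

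**The INR once close monitoring does apply.** For a baseline below 1.5 × ULN, a symptom-free value above 3 and below 5 × ULN falls under close monitoring only. Its repeat draw refers to Appendix 6, which lists PT-INR, and then names seven analytes, of which PT-INR is not one. Taken literally, the reference includes PT-INR. Against that, Appendix 6 speaks of selected tests that may be obtained. Section 8.2.5 also leaves several Appendix 6 tests merely to be considered at the severer tier, "including tests for hepatitis D virus, cytomegalovirus, Epstein-Barr virus, acetaminophen levels, acetaminophen protein adducts" among them. Counting rows: hepatitis D 1, cytomegalovirus 2, Epstein-Barr 2, acetaminophen 1, its adducts 1, urine drug screen 1, ethyl glucuronide 1, phosphatidylethanol 1, total 10. It would be odd to require these ten at the milder tier. Two careful sites could therefore differ on whether to draw an INR.

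**After the change.** For b from 1.5 to below 2, 2b is at least 3, so the lower of 2b and 3 is always 3. Both triggers then start at 3 × ULN and the band is empty for every such baseline.

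**The case against.** Several points on the other side are sound.

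- A reader might infer that a participant in this band gets no follow-up at all. The protocol does not support that. Section 8.2.4 asks that clinically significant abnormal values be repeated, that the cause be identified if they do not settle within a reasonable time, and that the sponsor then be told. Section 8 asks that immediate safety concerns be discussed with the sponsor. The gap lies in the specific hepatic pathway.
- A reader might infer that the INR is never drawn in a symptom-free participant with a normal or near-normal baseline at 3 to 5 × ULN. That is too strong: the reference to Appendix 6 arguably covers PT-INR already. This part is a wording ambiguity only.
- A reader might infer that 8.2.5 contradicts a stopping rule. Section 7.1 is a matter for consideration with the Medical Monitor and does not demand an INR at every value above 3 × ULN. In the symptomatic example its condition is met without one, so only symptom-free cases could lack an INR that matters.
- The table's first row reads ALT or AST below 1.5 × ULN. Taken literally, one enzyme below 1.5 places the participant in that row, with a trigger at 3 × ULN. The gap then needs both enzymes raised.
- Triggers relative to baseline are a legitimate choice: 3.5 from 1.9 is only 1.84 times baseline. Each ISA may also monitor more strictly, Appendix 2 permits extra tests at any time, and the ISAs are not before us.

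These points limit the weight of the finding. They do not remove the mismatch: the routes they name are general, discretionary or optional, and the master text is the common base for every ISA.

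**Conclusion.** The point holds in a narrow form. For baseline ALT/AST above 1.5 and below 2 × ULN, values above 3 × ULN and below twice baseline reach the Section 7.1 transaminase threshold without starting either tier of Section 8.2.5, unless TBL or ALP does so. It rests on reading the table analyte by analyte, or on both enzymes being at least 1.5 × ULN at baseline. The protocol gives no frequency for such participants, so no number affected can be stated, and ISA monitoring may already cover them. The PT-INR wording is a secondary clarification. Overall this is a minor safety point and a cheap improvement.

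**What to change.** In the close-monitoring table of Section 8.2.5, for baseline ALT or AST of 1.5 × ULN or more, set the trigger at the lower of 2 × baseline and 3 × ULN for participants covered by Section 7.1. Apply the same bound to the symptomatic comprehensive tier. Naming PT-INR alone would not be enough, because the 48-to-72-hour repeat and the serial monitoring would still not start in the band.

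As a clarification, name PT-INR among the tests of the 48-to-72-hour draw, so that the INR condition of Section 7.1 can be evaluated.

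The cost is a small change of protocol wording, plus a few extra repeat draws and evaluations in participants with raised baseline enzymes. PT-INR is already on the Appendix 6 list, for which central testing is foreseen.
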